- j. An electronic device will be provided to each subject at screening and the investigator/study-site personnel will provide sufficient information to enable the subject to complete the subject eCOA (including RI-PRO, additional questions about health and functioning, and HRQoL [EQ-5D-5L]). The subjects will complete the eCOA once daily throughout the study from screening to Day 28 at approximately the same time each day. If the subject is unable to complete the assessment on the device, the subject's spouse, partner, relative, friend or the investigator/study-site personnel trained on the eCOA device can read the questions and responses aloud to the subject, and enter the subject's responses in the eCOA device on the subject's behalf using the interview administration procedures explained in the eCOA completion guide. For Part 2, the questions will be read from the device for RI-PRO and additional questions about health and functioning, and from a paper form of the questionnaire provided to the caregiver by the site for HRQoL. If in the investigator's opinion, the subject (or the subject's spouse, partner, relative, or friend) is unlikely to reliably enter the information in the eCOA device on a daily basis for the duration of the study, the site will retain the eCOA device upon the

- subject's discharge and arrange for the investigator or trained study-site personnel to interview the subject by phone and record the subject's responses in the eCOA device on the subject's behalf each day post discharge to end of follow-up.
- k. The assessment on Day 1 must be recorded predose, before the LD. If the screening assessment was performed less than 8 hours prior to LD, the predose assessment does not need to be performed.
 - l. Clinical evaluation includes, but is not limited to, RSV disease symptoms, oxygen requirement (type, duration, and amount), level of hospital care, duration of hospitalization, respiratory rate, SpO₂, and body temperature.

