The ordinal scale consists of 6 categories that are exhaustive, mutually exclusive, and ordered (Table 6). For all subjects, the category at Day 5/6 (depending on the timing of the LD administration) will be established as the worst category on that day. For example, if a subject is discharged on Day 6, the category will be non-ICU and no supplemental oxygen (if there was no supplemental oxygen given on that day). The analysis will be performed using a proportional odds model, modeling the common odds ratio of the improvement on the ordinal scale of active treatment versus control. Baseline covariates that are predictive of the ordinal scale may be added to the model to increase the model fit. In case of missing data (>10%), a multiple imputation method under the missing-at-random assumption will be employed. Details will be provided in the SAP.

Table 6: Ordinal Scale on Day 5/6 (Depending on the Timing of the LD Administration)

Outcome
Death
Admitted to ICU
Non-ICU hospitalization requiring supplemental oxygen
Non-ICU hospitalization not requiring supplemental oxygen
Not hospitalized, unable to resume normal activities
Not hospitalized, resumption of normal activities

ICU = Intensive Care Unit

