4.1.1. Demographics and Baseline Characteristics

All demographics and baseline characteristics will be summarized overall and by treatment group. Descriptive statistics or frequency tabulation will be provided for the following parameters.

Demographic parameters:

Sex (Male, Female, Undifferentiated)

Race (White, Black or African American, Asian, American Indian or Alaska Native, Native Hawaiian or Other Pacific Islander, Other). The specification of the category ‘Other’ will only be listed.

Ethnicity (Hispanic or Latino, Not Hispanic or Latino)

Country (from [DM] dataset)

Geographic region (based on country: North America [to include Puerto Rico], Europe, South America, Asia-Pacific)

Age (years)

Weight at baseline (kg)

Height at baseline (cm)

BMI at baseline = Weight at baseline (kg) / (Height at baseline (m))²

(rounded to 1 decimal. Even if available in the raw data, BMI will be recalculated from baseline weight and height)

Baseline disease characteristics:

Duration of RSV symptoms prior to first treatment (days)

Presence of comorbidities (yes, no)

Comorbid diseases associated with risk for lower respiratory tract disease^{[1][2]} (yes, no) and proportion of subjects suffering from each of the following diseases:

- Asthma
- COPD
- CHF
- CAD (coronary artery disease)

Other conditions/therapy of potential interest due to risk of infections in general (yes, no) and proportion of subjects with each of the following conditions/therapies:

- Diabetes mellitus
- CRF (Chronic Renal Failure)
- Use of systemic corticosteroids (PO, IV) prior to or during the treatment

Baseline RSV Viral load (log₁₀ copies/mL)

Previous use of aerosolized ribavirin (yes, no)

Previous use of IV immunoglobulin (yes, no)

Oxygen Saturation (%)

Receiving Supplemental Oxygen (yes, no)

Intravenous or enteral tube feeding (yes, no)

Intravenous or enteral tube hydration (yes, no)

Respiratory Rate (breaths/min)

Heart Rate (beats/min)

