Time to normal temperature (hours) [Time-to event]	
Minimum[date and time of Time of return to pre-RSV disease level temperature, date and time of last measurement] - date and time of first dose of study drug)/3600[†], rounded to one decimal
 
If none of the values are abnormal for the subject, this value will be set at time 0.
 
Subjects with an abnormal value at the last assessment will be censored. Subjects for which this last assessment is the baseline assessment will be censored at time 0.

Time point of return to pre-RSV functional status (KATZ ADL score)	
The first time point where the KATZ ADL score is equal or higher than the pre-RSV disease KATZ ADL score and no lower scores are measured after this time point.
 
Functional status is the total points on the KATZ Index of Independence in Activities of Daily Living (KATZ ADL score)

Time to return to pre-RSV functional status (KATZ ADL score) (days) [Time-to-event]	
minimum[date and time of time of return to pre-RSV functional status, date and time of last measurement] - date and time of first dose of study drug)/3600, rounded to one decimal
 
If the KATZ ADL score is never lower than the pre-RSV score, this value will be set at time 0.
 
Subjects with a functional status lower than the pre-RSV disease functional status at the last KATZ ADL assessment will be censored. Subjects for which this last assessment is the baseline assessment will be censored at time 0.

Ordinal scale score	
The value as collected in the eCRF on the day of last dose (Day 5/6 depending on timing of LD) will be used as score on the day of last dose. Only in case of a missing score, the score will be calculated based on the available information in the eCRF.
 
The 6 categories to be considered are:

	
 • Death • Admitted to ICU • Non-ICU hospitalization requiring supplemental oxygen • Non-ICU hospitalization not requiring supplemental oxygen • Not hospitalized, unable to resume normal activities • Not hospitalized, resumption of normal activities 
Subjects will receive a score ranging from 1 (=subject died on or before of their day of last dosing) to 6 (=subject was not-hospitalized, resumption of normal activity) depending on his status on day of last dosing
 
For days 3 to 14, the ordinal scale will be calculated on each day, using the algorithm described above.

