If specified, time-to-events variables will also be compared between each active treatment group and placebo using an accelerated failure time (AFT) model. The distribution to be used will be determined based on the goodness of fit using Akaike's information criterion and will be selected from the following parametric families: lognormal, log-logistic, or Weibull. The AFT model will include the fixed, categorical effects for treatment (with placebo as the reference) and strata, as well as the continuous covariates of baseline \log_{10} viral load. Other covariates may be included when of predictive value, such as smoker (yes/no), presence/absence of co-morbid diseases, presence/absence of co-morbid diseases associated with risk for lower respiratory tract disease, presence/absence of other conditions/therapy of potential interest, days since symptom initiation, RSV subtype, use of corticosteroids, supplemental oxygen at baseline and age as continuous variable. As in the logistic regression, a significance level of 0.05 will be used for a variable to enter the model and a significance value of 0.10 to stay in the model. A summary of information from the final model will include parameter estimates and associated standard errors, estimated accelerated failure time ratios versus placebo and associated 95% confidence intervals, and p-values.

Length of Hospital Stay/Length of Hospital Need

The Length of Hospital Stay/Need (both since treatment initiation and since hospital admission) will be summarized and listed. The Length of Hospital Stay/Need will be analyzed in an exploratory manner using Kaplan-Meier analysis.

Length of Hospital Stay/Need will also be compared between each active treatment group and placebo using an accelerated failure time (AFT) model as described above.

Need and Duration of ICU Stay

The need for ICU stay will be analyzed on the subgroup of subjects who were not in the ICU before the first dose of study medication. The duration in the ICU will be analyzed all subjects and on both the subgroup who were and who were not in the ICU before the first dose of study medication.

The number and percentage of subject with need of ICU stay, and the duration of ICU stay in hours, will be summarized descriptively.

To compare incidence of the need for ICU stay across treatment groups, (exact) logistic regression as described before will be used.

Need and Duration of Oxygen Support, Supplemental Feeding, Supplemental Hydration

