The time to return to pre-RSV disease level (hours) for RR, SpO₂ and body temperature will be analyzed using the same approach as for the Time to SpO₂ ≥ 93% (hours) on room air.

Time to return to pre-RSV functional status (KATZ ADL score) (days)

Time to return to pre-RSV functional status (KATZ ADL score) (days) will be analyzed using the same approach as for the Time to SpO₂ ≥ 93% (hours) on room air.

Time to clinical stability (hours)

The time to clinical stability (hours) will be analyzed using the same approach as for the Time to SpO₂ ≥ 93% (hours) on room air.

Ordinal scale

The number and percentage of subjects will be summarized for the ordinal scale by treatment group at the end of the treatment period (Day 5/6).

The analysis will be performed using a proportional odds model, modeling the common odds ratio of the improvement on the ordinal scale of each active treatment versus control. Age category (≥50 to <65 years and ≥65 years) and region (Japan, non-Japan) will be added to the model as fixed factors. For each of the 5 possible cut-points the odds ratio will also be presented (comparing active versus placebo) to verify the common odds assumption.

For the ordinal scale also descriptive statistics will be computed for each post-baseline day (days 3 to 14 and day of last dose). Here missing data will be imputed using the LOCF approach.

All-cause mortality

The number and percentage of subjects who died will be summarized and compared between treatment groups using the logistic regression approach described before.

Note that this analysis will only be performed if any deaths did occur.

Viral load over time

Descriptive statistics and mean (SE) plots will be shown for the log₁₀ values of RSV RNA viral load and the changes from baseline calculated in log₁₀(copies/ml) by treatment group.

Peak viral load/Rate of decline:

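### The ordinal-scale model adjusts only for age category and region and does not use the protocol's option to add baseline respiratory status, which is already recorded and likely prognostic

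*SAP*

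**What the plan says.** - **Model.** SAP 4.2.4.2 (Ordinal scale) uses a proportional odds model, "modeling the common odds ratio of the improvement on the ordinal scale of each active treatment versus control". Age category "and region (Japan, non-Japan) will be added to the model as fixed factors". No other covariate and no selection step is named for this endpoint.
- **Protocol.** Section 11.3 is permissive: "Baseline covariates that are predictive of the ordinal scale may be added to the model to increase the model fit". It names no covariate and defers details to the SAP.
- **Outcome.** In SAP 4.2.4.1, three of the six categories separate patients in hospital by ICU and oxygen use. One of them is "Non-ICU hospitalization requiring supplemental oxygen".
- **Baseline data.** SAP 4.1.1 lists receipt of supplemental oxygen as a baseline characteristic. The clinical evaluation in the protocol's Time and Events Schedule (footnote l) covers "oxygen requirement (type, duration, and amount), level of hospital care" and is done at screening and on Day 1.
- **Other secondary models.** The logistic, accelerated failure time and linear models in SAP 4.2.4.2 all include "supplemental oxygen at baseline and age as continuous variable" among their optional candidates. The need-for-ICU analysis is restricted to "subjects who were not in the ICU before the first dose of study medication".

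**The concern.** Inclusion criterion 2 requires subjects to be in hospital, or in the emergency room before hospitalization, at randomization. Nearly all therefore start in one of three states: ICU, oxygen outside the ICU, or no oxygen. The outcome uses the same distinctions about five days later, so the starting state is a plausible predictor of the result. It is a candidate covariate for peak viral load but not for the endpoint it helps to define.

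Two things are at stake. In a proportional odds model, omitting a prognostic covariate lowers the power of the treatment test. And randomization is stratified only by region and age, so with about 30 subjects per arm a chance difference in baseline severity is corrected neither by design nor by analysis.

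**Working it through.** **1. The plan's own power figure.** SAP 1.4 states about 90% power at an effect size of 0.77 and about 80% at 0.67, for the viral-load AUC with 90 subjects. The check took the larger of the two contrasts, (-1, 0.5, 0.5) and (-1, 0, 1), whose correlation is 0.866, at one-sided 0.025 with 30 per arm and the full effect in both active arms. A single look gives 90.5-91.0% and 81.0-81.8%. A three-look O'Brien-Fleming design gives 91.3-91.4% and 82.3-82.5%. The stated figures reproduce. They concern the primary endpoint; no power is stated for the ordinal scale.

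**2. Inputs for the ordinal scale.** From the documents: 30 per arm, six categories, a proportional odds model with age category and region. Assumed, because the documents give no figure:
- baseline mix of 10% ICU, 60% oxygen, 30% neither;
- outcome mix from death to normal activities of 3/7/25/20/25/20%;
- 60% in the older age band (log-odds effect -0.3) and 20% from Japan;
- conditional treatment odds ratio (OR) of 2.5 or 3.5;
- OR per baseline step (ICU to oxygen, oxygen to neither) from 1 to 10.

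**3. Power for one active arm v placebo.** Likelihood-ratio test at two-sided 0.05, with 1,200-1,500 simulated trials per cell. The standard error of each power is at most √(0.25/1,200) = 1.4 points.

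| Treatment OR | OR per baseline step | Without baseline term | With baseline term | Gain (points) |
|---|---|---|---|---|
| 2.5 | 1 (none) | 50.8% | 50.5% | -0.3 |
| 2.5 | 1.5 (weak) | 51.7% | 52.3% | 0.7 |
| 2.5 | 3 (moderate) | 44.5% | 49.9% | 5.5 |
| 2.5 | 6 (strong) | 40.8% | 51.4% | 10.6 |
| 2.5 | 10 (very strong) | 32.4% | 50.3% | 17.8 |
| 3.5 | 3 | 70.6% | 75.3% | 4.8 |
| 3.5 | 6 | 59.4% | 71.9% | 12.5 |
| 3.5 | 10 | 52.3% | 74.3% | 22.0 |

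With no treatment effect, rejection is 5-7% with or without the term.

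**4. A second set of assumptions.** Baseline 57% oxygen and 8% ICU, treatment OR 2.5. Log-odds effects for oxygen and ICU are 1.6 and 3.0 (stronger) or 1.0 and 2.0 (weaker). Power without → with the three-level baseline term:
- stronger: 43% → 52% (250 trials), 42% → 50% (600), 41% → 49% (500);
- weaker: 48% → 51%, 45% → 49%, 47% → 53%.

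The gain is 8-9 points in the stronger case and 3-6 in the weaker. The 250-trial figures have a standard error of about 3 points. With no prognostic effect, power is 46% v 47% (300 trials).

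**5. A binary term.** Oxygen or ICU v neither gives 50% and 49% in the 600-trial runs, equal to the three-level term. In the 500-trial runs it gives 47% and 51%, which is 6 of 8 and 4 of 6 points of the gain. At 8-10%, ICU means 0.08 × 30 = 2.4 to 0.10 × 30 = 3 subjects per arm.

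**6. Chance imbalance.** Suppose a proportion p of subjects are on oxygen at baseline (assumed 50-70%). The difference D between two arms of 30 has standard deviation √(2 × 30 × p(1 - p)), which is 3.87 at p = 0.5 and 3.55 at p = 0.7. With a continuity correction, P(|D| ≥ 5) ≈ 2[1 - Φ(4.5/SD)], or about 25% and 20%. Five of 30 is 17 percentage points.

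**7. Odds ratio.** The true conditional log OR is ln 2.5 = 0.92. At 6 per baseline step, the median estimate is 0.83 without the term and 1.02 with it. The 500-trial runs give 0.85 and 0.97.

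**The case against.** **The SAP does not forbid the covariate.** Section 1 says it is to be read with the protocol, and the ordinal-scale text does not say that age and region are the only terms. A reader might infer that the SAP overrides the protocol's permission, but the wording does not go that far. What remains is that neither document says whether or how the permission will be used. The term will either be left out or be chosen without prespecification.

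**Prognostic strength is not documented.** This stands in full. No passage gives the baseline mix or its relation to the Day 5/6 category. The omission is certain; its size is not, and it is negligible if the predictor is weak.

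**The smaller unadjusted odds ratio is not a bias.** A reader might infer that omitting the term wrongly pulls the estimate towards 1. Odds ratios are non-collapsible, so the marginal and conditional odds ratios are different quantities. The adjusted medians also sit above 0.92, which points to small-sample error. The case rests on power and imbalance.

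**Baseline severity is handled in the component endpoints.** SAP 4.2.4.2 analyses oxygen need and duration separately by oxygen use before treatment, and splits the ICU analyses by ICU status before first dose. This is true, but none of it carries over to the ordinal scale.

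**The consequence is limited.** The scale is one of many secondary endpoints. Under randomization, chance imbalance costs precision, not validity.

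**Conclusion.** The point holds as a worthwhile improvement to a secondary analysis. Under the assumptions shown, omitting baseline respiratory status costs roughly 3 to 12 points of power at 30 v 30 if it is moderately to strongly prognostic (the largest such cell is 12.5) and about 0 to 1 point if it is weak. The 18 to 22 point losses need a very strong predictor and should not be taken as the expected size. Including the term cost essentially nothing in any scenario examined.

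A reader might infer that the trial is underpowered or that its type 1 error is at risk. The documents do not support either. No power is claimed for this endpoint, 90 subjects were justified on the primary endpoint and that figure reproduces, and null rejection is about the same with and without the term. Confidence is high on the omission and moderate at most on its size.

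**What to change.** In SAP 4.2.4.2 (Ordinal scale), name baseline respiratory status as a fixed factor with age category and region, not subject to stepwise selection. Make it binary: supplemental oxygen by any method or ICU, v neither, taken from the last record before first intake as SAP 2.1 defines baseline. This avoids a sparse ICU level, needs no rule for merging categories, and recovers most or all of the gain. State that the common odds ratio is then conditional on baseline status, a different estimand from the odds ratio without that term.

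The cost is SAP wording, agreed before unblinding. The data are already collected and no protocol change is needed, since protocol 11.3 already allows it. The same sentence needs revision anyway: its younger age band starts at 50 years, while protocol Section 5 stratifies Part 2 from 18 years.

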4.2.1.1. Level of Significance

The primary hypothesis is a positive dose-response relationship for the AUC of active treatment regimens. The positive dose-response relationship assumes that dose regimens with higher exposure with respect to MD will have at least an equal or better effect on viral load. Therefore 2 contrasts will be tested at each of the interim analysis points and final analysis; a contrast with no difference between the 2 active regimens tested against placebo and a contrast with a positive linear dose-response relationship with respect to active regimens. With respect to multiple contrast testing, multiplicity will be controlled at the prespecified (interim) alpha level by calculating adjusted p-values from the simulated distribution of the maximum or maximum absolute value of a multivariate t random vector (ie, using the correlation between the contrasts to optimally control for alpha)¹. The overall (family-wise) type 1 error rate of 2.5% (1-sided) will be adjusted for multiple testing due to formal interim analyses using an O'Brien-Fleming alpha spending function with 3 sequential tests (2 interim, 1 final)⁵.

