4.2.3.2. Analysis Methods

Mean \log_{10} viral load values over time will be analyzed using a restricted maximum likelihood based repeated measures approach. Analyses will include the fixed, categorical effects of treatment, strata, visit, and treatment-by-visit interaction, as well as the continuous, fixed covariates of baseline \log_{10} viral load and baseline \log_{10} viral load by-visit interaction. An unstructured covariance structure will be selected. In case this model will not converge, the

following list of covariance structures will be applied and a selection will be based on the Akaike Information Criterion for those that do converge:

- Unstructured [UN]
- Ante-dependence [ANTE(1)]
- Heterogenous Toeplitz [TOEPH]
- Heterogeneous CS [CSH]
- Heterogeneous AR(1) [ARH(1)]
- Toeplitz [TOEP]

The Kenward-Roger approximation will be used to estimate denominator degrees of freedom.

The testing of the dose-response relation is based on the expectation that higher dose regimens will be at least as efficacious as lower dose regimens with respect to efficacy on the viral load over time. Therefore, two contrasts on the dose regimens have been selected that are consistent with this expectation: a contrast with no difference between the 2 active regimens tested against placebo and a contrast with a positive linear dose-response relationship with respect to active regimens. A multiple comparison approach will be taken testing the 2 contrasts combined versus placebo, adjusted for multiplicity.

The SAS mock code used to test the primary hypotheses will be as follows:

```
proc mixed data=viral_load;
  where avisitn in (2,3,4,5,6,7)
  class avisitn trt usubjid stratum;
  model logtiter = trt|avisitn stratum base|avisitn /ddfm=kr s;
  repeated avisitn/subject=usubjid type=un;
  lsmestimate trt*avisitn
  "Plateau" -4 2 2 -4 2 2 -4 2 2 -4 2 2 -4 2 2 -2 1 1,
  "Linear" -4 0 4 -4 0 4 -4 0 4 -4 0 4 -4 0 4 -2 0 2
  /divisor=4 adjust=simulate seed=3369 alpha=alpha* lower cl;
run;
```

The variable *trt* denotes the *placebo*, *low dose regimen*, and *high dose regimen* treatment groups, the *avisitn* variable denotes the swabbing visits at Days 2 through 7, and the *base* variable is the baseline log₁₀ viral load measured at Day 1.

The significance level of *alpha* (α^*) will have to be calculated based on the information fraction at the time of the test using the pre-specified O'Brien-Fleming (OBF) α spending function.

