$$\alpha^*(t') = 2 - 2\phi(Z_{\alpha/2} / \sqrt{t'})$$

where $t' = n/N$, n is the ITT-i set size and N is the expected ITT-i set size at the end of study (=90) and ϕ denotes the standard normal cumulative distribution function.

The *lower* option is selected as the contrast needs to have a value below zero (ie, there needs to be a reduction in AUC comparing active treatment to placebo). In summary, a positive dose-response relationship will be concluded if based on this analysis for any of the two estimations the resulting adjusted p-value is lower than the associated OBF critical value.

The differences in the AUCs for active versus placebo will be derived using appropriate contrasts deriving least square mean differences, including the 95% 2-sided confidence intervals.

The individual AUC as calculated using the trapezoidal rule will be considered as a supportive analysis and will be analyzed using a linear model with AUC as a dependent variable and treatment group and stratum as fixed factors, and baseline log₁₀ viral load as fixed covariate. For this analysis no adjustments for multiplicity will be applied, that is the differences versus placebo will be estimated using appropriate contrasts with 95% confidence intervals.

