The proportion of subjects with a negative viral shedding titer will be tabulated at each timepoint (with corresponding 95% CI). In addition, the same logistic regression approach as described before will be used to obtain the odds ratios (95% CI) for each comparison versus placebo.

RSV RNA viral load AUC until Day 10 and until Day 14

The same model used for the primary analysis will be used to test for a dose response relationship on the AUC until Day 10 and until Day 14. No corrections for multiplicity will be made, thus the significance level of α (α^*) will be kept at 0.05.

The differences in the AUCs for active versus placebo will be derived using appropriate contrasts deriving least square mean differences, including the 95% 2-sided confidence intervals.

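### For AUC to Day 10 and Day 14 the SAP sets α* at 0.05 without stating sidedness, while reusing a primary model whose contrast test is one-sided

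*SAP*

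**What the plan says.** SAP 4.2.4.2, in the paragraph on AUC until Day 10 and until Day 14, says: "The same model used for the primary analysis will be used to test for a dose response relationship on the AUC". It adds that "No corrections for multiplicity will be made" and, as a consequence, that the level α* "will be kept at 0.05". The paragraph then asks for active-versus-placebo AUC differences with 95% two-sided confidence intervals.

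α* is defined in SAP 4.2.3.2. It is the alpha in the contrast statement of the primary SAS code, whose options read "divisor=4 adjust=simulate seed=3369 alpha=alpha* lower cl". The text explains that the LOWER "option is selected as the contrast needs to have a value below zero", so the test is one-sided. The same code defines a plateau contrast (both active arms against placebo) and a linear contrast, whose weights are zero for the low dose and equal and opposite for placebo and high dose.

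SAP 4.2.1.1 gives the error rate for the primary hypothesis: "The overall (family-wise) type 1 error rate of 2.5% (1-sided) will be adjusted for multiple testing due to formal interim analyses". SAP 1.4 and Protocol 11.2 give the same rate. Neither document says whether the 0.05 for Day 10 and Day 14 is one-sided or two-sided.

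**The concern.** The reason given for 0.05 does not lead to 0.05. Removing the interim-analysis correction from a 2.5% one-sided procedure leaves 2.5% one-sided. The primary analysis has no 0.05 level to keep. The figure looks like a two-sided convention placed in a one-sided procedure.

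A programmer who follows the two sections as written would run the contrast statement with alpha at 0.05 and LOWER still in place. AUC to Day 10 and to Day 14 measures the same antiviral effect as the primary endpoint over a longer period, so readers will see these results as support for it. They would be judged by a looser criterion than the primary, and one that can disagree with an interval reported alongside it.

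**Working it through.** **Inputs.** From the SAP: 90 subjects randomized 1:1:1, so 30 per arm (1.4); plateau contrast (−1, 0.5, 0.5) and linear contrast (−1, 0, 1) for placebo, low dose and high dose (4.2.3.2); primary level 2.5% one-sided (4.2.1.1); α* = 0.05 for these endpoints (4.2.4.2). Assumed: about 85 degrees of freedom, and Day 10 and Day 14 contrasts that keep the primary form.

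**The plan's own figure.** The SAP states about 90% power at d = 0.77 and 80% at d = 0.67. With 2.5% one-sided, O'Brien-Fleming spending, looks assumed at 50%, 75% and 100%, and both active arms assumed at d, simulation gives 90.7% and 81.1%. The stated power is thus reproduced at 2.5% one-sided. It does not by itself identify the level: a linear effect shape at 5% one-sided gives 88.1% and 79.0%. The 2.5% rests on the explicit text.

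**What removing the interim correction leaves.** The spending formula in 4.2.3.2 is α*(t′) = 2 − 2Φ(z_{α/2}/√t′). At t′ = 1 it returns α, so α = 0.025 gives 0.025.

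**Correlation of the contrasts.** (1 + 0 + 0.5)/√(1.5 × 2) = 1.5/1.732 = 0.866.

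**Error rates per time horizon under no effect:**

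| | α* = 0.05 one-sided | α* = 0.025 one-sided |
|---|---|---|
| Each contrast, unadjusted | 5.0% (critical t 1.663) | 2.5% (critical t 1.988) |
| Either contrast, adjust=simulate kept | 5.0% (critical t 1.837) | 2.5% (critical t 2.158) |
| Either contrast, adjust=simulate dropped | about 7.1% | about 3.7% |

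The last row is from 2,000,000 simulated null trials on the normal scale; the t-based version gives 7.0% and 3.6%.

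**Test against interval.** The linear contrast is exactly high dose minus placebo, one of the differences for which a 95% two-sided interval is reported. That interval excludes zero in the favourable direction only if t exceeds 1.988. On the literal reading the two disagree when:

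- t is between 1.663 and 1.988 without the adjustment; null probability 5.0% − 2.5% = 2.5%.
- t is between 1.837 and 1.988 with the adjustment; null probability 3.48% − 2.5% ≈ 1.0%.

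**Example, unadjusted.** With 30 per arm the standard error is √(2/30) = 0.258 SD. At t = 1.80 the difference is −1.80 × 0.258 = −0.465 SD and one-sided p = 0.038, which is significant at 0.05. The 95% interval is −0.465 ± 1.988 × 0.258, that is −0.978 to +0.049 SD, which includes zero.

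**The case against.** The strongest reply is that 0.05 is simply the conventional two-sided level. The paragraph never calls it one-sided, and its next sentence specifies two-sided 95% intervals. On that reading nothing doubles and the linear test agrees with its interval. This is plausible and cannot be excluded, so a reader who infers that the tests certainly run at twice the primary level goes further than the text allows. What remains is that the text assigns 0.05 to α*, and α* sits beside LOWER in the model being reused. The wording needs correction on either reading.

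Three other strong inferences also lack support.

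- **That the false-positive rate is 7.1%.** This holds only if the disclaimer also removes adjust=simulate. The sentence ties the disclaimer to α*, which carries the interim correction, and the reused code contains adjust=simulate. If that option stays, the rate is 5.0%.
- **That both contrasts can contradict their own intervals.** Only the linear contrast equals a reported difference. No interval is specified for the plateau contrast.
- **That the trial's error control is breached.** The 2.5% one-sided family-wise rate is stated for the primary hypothesis. These endpoints are secondary, and the SAP openly makes no multiplicity claim for them, which is acceptable in a dose-finding trial.

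It is also fair to say that test and interval levels differ in the primary analysis, where an adjusted test is paired with 95% pairwise intervals. There, however, the test is the stricter of the two (critical t at least 2.158 against 1.988), so a significant linear contrast cannot sit beside an interval that includes zero. On the literal reading of the Day 10 and Day 14 rule, it can.

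**Conclusion.** The point stands in limited form. As written, the AUC to Day 10 and Day 14 contrasts are tested at 5% one-sided, against 2.5% one-sided for the primary. If two-sided 0.05 was intended, the SAP omits this and keeps an option that contradicts it.

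The size depends on an option whose fate the paragraph leaves unclear: 5.0% per time horizon with adjust=simulate, about 7.1% without it. The conflict with a reported interval is confined to the linear contrast, within the t ranges worked out above. Those ranges assume about 85 degrees of freedom and would shift slightly with the Kenward-Roger value. The primary type I error, sample size and stopping rules are untouched. The fault is an inconsistent criterion for a secondary claim, which should be corrected before the analysis is run.

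**What to change.** In SAP 4.2.4.2, set α* = 0.025 one-sided for the AUC to Day 10 and Day 14 contrasts. Alternatively, drop LOWER for these endpoints and test two-sided at 0.05. Either choice gives an unadjusted critical t of 1.988 in the favourable direction, the same cut-off as the 95% interval.

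In the same sentence, state whether adjust=simulate is retained for the two contrasts. At 0.025 one-sided, this decides whether the either-contrast error per time horizon is 2.5% or about 3.7%.

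The cost is a sentence in the SAP, and secondary results become slightly harder to call positive. No new data are needed, and the primary analysis and sample size do not change.
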